**Serological Testing:** Serology will establish background immunity levels in students and staff, from infection or vaccination, and will follow those who are antibody-positive longitudinally to quantify temporal decay of IgG and neutralizing antibody levels. We will determine whether protective immunity in children with IDD, a population with prevalent immunological dysfunction, wanes at an accelerated rate compared to the population-at-large; by doing so we will address an important knowledge gap, and provide key data to inform public health policy. **3) Modeling to Optimize Testing:** We will use network models and agent-based simulation models (or hybrid approaches) to guide testing strategies and interventions at MCC. Simulations will be conducted interactively and iteratively, to assist in planning and implementation of testing procedures, exploring the dynamic interplay between school operations and personnel interactions, potential infection risks and disease dynamics (including variant strains), and implementation of control measures (e.g. quarantine, isolation, contact-tracing and vaccination rates). **4) Mobile Unit Testing:** We build on our successful mobile approach to delivering mobile dental care to the IDD students of MCC (the SMILEmobile), by staffing, equipping and deploying a customized, disability-enabled, mobile testing unit equipped with a specialized HEPA-filter enabled HVAC system (**UR Health in Testing - HIT Mobile**). We will use this to directly deliver rapid flexible testing to MCC. **5) Overcoming Testing & Vaccine**

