#### **1.4 CENTRAL AIMS**

**Scientific Goal 1: Establish a molecular testing program to monitor and identify COVID-19 infections within a school community of individuals with IDD**

**Overview and rationale:** This program will focus on the students (n=450) and staff (n=500) of the MCC, who collectively form a community that is highly representative of other IDD school communities across the nation. We will establish testing across this difficult-to-test population, using a tailored and flexible approach to foster test uptake and to prevent and/or mitigate COVID-19 outbreaks.

**Establish a clinical molecular and serological COVID-19 testing program for the Mary Cariola Center:** The dynamics of viral spread are unknown in a school serving individuals with IDD such as the MCC. Questions to be answered with *molecular* testing include: What is the incidence of asymptomatic COVID-19 infection, and how is this affected by rising vaccination rates? How do activities within the school alter risk? *Serological* testing will assess baseline prevalence of prior infection (anti-NP IgG), and changes over time, in response to infection (anti-NP IgG+) and vaccination (anti-S IgG+, anti-NP IgG-).

**Molecular Testing:** RT-PCR tests for SARS-CoV-2 with FDA EUA will deliver highly sensitive and specific clinical-grade results. Respiratory samples will be obtained by mid-turbinate or nasal swabs, collected in a dedicated area with proper ventilation and PPE (see Mobile Unit testing plan below), and delivered to the URMC Central Laboratory for testing in a CLIA environment with 24-72h turnaround times. The testing plan includes two groups: those tested as part of scheduled surveillance and those tested for symptoms or exposure.

**Surveillance Screening and Exposure/Symptomatic Testing:** Participants will be tested every 5-14 days to increase likelihood of detecting infected but asymptomatic individuals. Enrolled students and staff who report symptoms in the on-site screening will be tested on-site. Symptomatic individuals will be tested separately from asymptomatic participants every 3 days for up to 10 days. *Reported* test results will be qualitative, although Ct (cycle threshold) values will also be captured for modeling purposes.

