### Scientific Goal 2: Serological Testing and Modeling

The dynamics of the immune response to SARS-CoV-2 are as yet unknown in children with IDD, a population with prevalent immunological dysfunction, who may show different COVID-related immunological profiles and latencies to those of the general population. Here, we longitudinally follow those with IDD identified as antibody-positive, from either infection or vaccination, to quantify the timing of reductions in IgG and neutralizing antibody levels. We will use a combination of the SARS-CoV-2 clinical serological assay (described above), and a research multiplex assay for anti-spike and nucleocapsid protein IgG and receptor binding domain (RBS) antibodies, against SARS CoV-2 (including emerging virus variants), and a panel of commonly circulating human coronaviruses. *This will provide serological data uniquely focused on the IDD population with clear implications for public health immunity strategies.*

**Experimental Approach.** IgG responses to individual SARS-CoV-2 antigens (S, NP, RBD) in enrolled students and staff will be measured initially by clinical testing and fingerstick at baseline, and then every four weeks by fingerstick for up to 36 months. Any large increase in anti-SARS-CoV-2 levels will be confirmed by clinical serology. Dynamics of anti-SARS-CoV-2 IgG will be assessed by fitting the anti-S, NP and RBD quantitative results to a modified power law model that accounts for long-term antibody persistence:  $f(t) = k + \log [(1 - \lambda)(c + t)^{-\alpha} + \lambda]$ , where  $k$  is the peak log IgG level,  $\alpha$  is the decay rate,  $c$  is a constant, and  $\lambda$  is the steady-state long-term IgG level. We will fit the model using a mixed effects

**Figure 1 – Serological Testing.** (A) Clinical analysis of persistence of anti-S, anti-NP, and anti-RBD binding IgG and PCR results from the URMC Clinical Laboratory. Note the early decline of anti-NP IgG. (B) Multiplex testing for IgG directed against S proteins for common circulating coronaviruses, including SARS-CoV-2 (SARS2), and prior SARS-CoV-1 and MERS (Middle East Respiratory Virus)

method, where  $k$  and  $\alpha$  are subject specific random effects drawn from a bivariate normal distribution. This will allow comparison of decay rates ( $\alpha$ ) and steady state anti-SARS-CoV-2 IgG levels ( $\lambda$ ) across subjects.

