#### **Asymptomatic Testing –**

**Nasal Swab:** Participating individuals (students and employees) will be tested for COVID-19 (RT-PCR) using a specimen collected using a mid-turbinete swab. This asymptomatic testing

STUDY #: 5294

Version Date: 04/17/2023

Page 13 of 27

regime starts on or after (if scheduling testing requires this to begin on a different day) enrollment and is repeated every 5-14 days for up to 36 months. Anyone testing positive is followed up as described below for symptomatic individuals.

**Saliva Sample:** For those participants (students only) that are unable to tolerate the nasal swab (mid-turbinate) test, we will use the Spectrum Solutions™ SDNA-1000 Molecular Diagnostic Saliva Collection Device. This is a self-contained, **EUA authorized** saliva collection system. It requires filling a small tube with saliva.

**Blood Samples:** Participating asymptomatic individuals (students and employees) will be tested for antibodies using the fingerstick upon scheduling first sampling visit and monthly thereafter for up to 36 months. This first blood sampling will be using a fingerstick and 1-2 drops of blood will be collected in a curette for serology testing. Possible complications include pain from the fingerstick, and a low risk of infection. The rationale for this intervention is to measure serum antibodies against SARS-CoV-2 using standard FDA approved testing methods.

A second method for blood sampling using venipuncture will be carried upon enrollment or upon scheduling the first sampling visit and subsequently, every six months for up to 36 months. In addition this method will be used for additional blood collection for MBC and DNA analyses. This second method will use venipuncture to collect ~6-10 cc of whole blood (except in students younger than 5 years in whom we will collect between 3-5cc). The possible complications of phlebotomy/venipuncture include pain, small local hematoma formation, bleeding and infection. However, this method of blood collection and testing is widely used by millions individuals daily in the United States with minimal complications, including IDD subjects. Phlebotomy will be conducted by a team specially trained in working with IDD subjects to minimize risk.

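### The Goal 2 antibody model gives λ one value for everyone yet promises to compare it, and states neither a time origin nor a re-exposure rule for a curve that can only fall

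*Protocol*

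**What the plan says.** The model is in the protocol, section 1.4, Scientific Goal 2 (Experimental Approach). Anti-S, anti-NP and anti-RBD IgG are fitted to f(t) = k + log[(1−λ)(c+t)^(−α) + λ] by a mixed-effects method. The parameter k "is the peak log IgG level" and λ "is the steady-state long-term IgG level"; c is called a constant. Of k and α the protocol says that they "are subject specific random effects drawn from a bivariate normal distribution. This will allow comparison of decay rates". The same sentence adds λ to the quantities to be compared across subjects.

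On who is followed, the protocol writes "we longitudinally follow those with IDD identified as antibody-positive, from either infection or vaccination". On timing, section 4.1 has the "fingerstick upon scheduling first sampling visit and monthly thereafter for up to 36 months". On rising levels the only sentence is "Any large increase in anti-SARS-CoV-2 levels will be confirmed by clinical serology".

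The question behind the model is in section 1.3: whether immunity in children with IDD "wanes at an accelerated rate compared to the population-at-large". The SAP names no model. It says that the time course of the immune response will be evaluated, and it places the primary analysis on the spread of infection.

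**The concern.** Three features do not fit together.

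- λ is to be compared, but nothing in the model lets it vary.
- λ is described as an IgG level, but in the formula it acts as a fraction.
- The curve describes one decline from one peak. The protocol expects new exposures during follow-up (Contingency Plans anticipates vaccine approval for under-16s, and the adverse-event section expects some subjects to test positive). It also follows people who were already antibody-positive when identified. Neither document says where t starts or what happens to a subject's series after a new exposure.

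α and λ are the only stated model quantities that could answer the waning question. If λ cannot be compared, and α absorbs differences in plateau, entry time or boosting, the answer on waning is hard to interpret.

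**Working it through.** **Inputs from the documents.** The formula and its random effects (Goal 2); 200 subjects sampled every 4 weeks for up to 36 months (Research Serological Testing). 36 × 30.44 / 28 = 39.1 intervals, so 40 samples, the last at 39 × 28 = 1,092 days, or month 35.9. The documents give no value for α, λ, c, variances, boosting or lag, and no power figure for this analysis, so there is no stated figure to reproduce.

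**Algebra (no assumed numbers).**

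1. With k_i and α_i subject-specific and λ common, λ_i − λ_j = 0 for every pair by construction.
2. As t grows, (c+t)^(−α) → 0 and f(t) → k + log λ. So λ is a fraction on the scale set by k. With one λ, modelled long-term levels differ between subjects only through k.
3. f(0) = k + log[(1−λ)c^(−α) + λ]. This equals k for every α only if c = 1, so the meaning of k as the peak depends on how c and the unit of t are set.
4. f′(t) = −α(1−λ)(c+t)^(−α−1) / [(1−λ)(c+t)^(−α) + λ], which is negative for α > 0 and 0 < λ < 1. The curve cannot describe a second rise.

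**Illustration (all parameter values assumed).** 100 students and 100 staff, 40 four-weekly samples, c = 1 month, mean α = 1.0 (SD 0.15), equal mean k (SD 0.5), residual SD 0.2, natural logs. Marginal maximum likelihood, λ estimated, medians of 30 datasets.

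*Shared λ.*

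| True λ, group 1 vs 2 | Fitted α, group 1 vs 2 |
|---|---|
| 0.02 vs 0.06 | 1.03 vs 0.71 |
| 0.02 vs 0.04 | 1.03 vs 0.86 |
| 0.02 vs 0.03 | 1.03 vs 0.95 |
| equal | 0.99 vs 1.00 |

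With λ by group, the first case returns α 1.00/1.00 and λ 0.020/0.060.

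The first case on noise-free mean curves gives α 1.039 vs 0.723, k 0.020 vs −0.218 and shared λ 0.024. At the last visit, c + t = 36.9:

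- True levels: 0.98/36.9 + 0.02 = 4.7% and 0.94/36.9 + 0.06 = 8.5% of the t = 0 level; log ratio +0.61.
- Modelled: 0.976 × 36.9^(−1.039) + 0.024 = 0.047 and 0.976 × 36.9^(−0.723) + 0.024 = 0.096; log ratio +0.71, plus the k difference of −0.24, gives about +0.47.

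*Time origin.* Identical true curves (λ = 0.04), with t counted from enrolment:

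| Enrolment after peak, group 1 vs 2 | Fitted α, simulated | Fitted α, noise-free |
|---|---|---|
| 0 vs 3 months | 0.99 vs 0.49 | 1.00 vs 0.50 |
| 3 vs 3 months | 0.43 vs 0.43 | 0.44 vs 0.44 |

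Counting t from the peak returns 0.99–1.01.

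*Boosting.* One curve drawn through a boost back to peak, λ = 0.04 in both groups:

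| Boosted, group 1 vs 2 | Boost timing | Fitted α, group 1 vs 2 |
|---|---|---|
| 20% vs 60% | months 6–12 | 0.78 vs 0.73 |
| 20% vs 60% | months 18–30 | 1.23 vs 1.67 |
| 40% vs 40% | months 6–30 | 1.18 vs 1.16 |

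Ending the series at the boost returns 1.00–1.01.

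**The case against.** The protocol never says that λ is common. A covariate on λ, or separate fits for students and staff, would be compatible with its text. That is so, but neither is stated, and the sentence credits the λ comparison to the random effects on k and α. The point therefore concerns the model as written; a modest extension would allow the comparison.

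A reader might infer that a shared λ ranks the groups wrongly on long-term antibody. Within follow-up it does not. In the illustration the modelled order is right from month 6 through month 36. It reverses only after about 800 months, so the misordering belongs to the extrapolated limit. Nor does the shared λ invent a waning difference: the lower α goes to the group that truly retains more antibody, so what is lost is the attribution between decay rate and plateau.

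A reader might also take the halved α as the expected error. It arises only if t is counted from enrolment. Calling k the peak points to an origin at the peak, and that origin removes the bias. What stands is that the origin is only implied, and that people already antibody-positive at entry may have no datable peak.

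The boost figures change direction with timing and rest on assumed unequal rates, so no direction of bias can be claimed. The student/staff contrast is itself a reading: Goal 2 speaks of subjects, and section 1.3 of the general population. Staff are simply the comparison group the study has.

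Finally, much of what a re-exposure rule needs is already planned: PCR every 5–14 days, four-weekly IgG, clinical confirmation of large rises and recording of vaccination. That makes the rule cheap to write but does not supply it.

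**Conclusion.** The structural points hold on the protocol's own text. The pooled model as written cannot compare λ; λ is mislabelled; the curve cannot rise; and the time origin and the handling of re-exposure are not stated.

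The sizes are illustrative only. If λ truly differed threefold (0.02 vs 0.06), α would be misstated as about 1.03 vs 0.71, and the last-visit log difference understated at about +0.47 against +0.61. If t were counted from enrolment with entry 0 vs 3 months after peak, α would be about 1.0 vs 0.5 for identical curves. Equal lag or equal boosting biases both groups alike, leaving little or no contrast between them.

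The documents do not show whether students and staff differ in λ, lag or boosting, so a biased contrast is a risk and not a demonstrated result. Goal 2 is not the SAP's primary analysis. This should be fixed before the decay model is fitted; it does not threaten the study as a whole.

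**What to change.** In Goal 2 and in the SAP:

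1. Give λ a student/staff effect (or a random effect on logit λ) and α a matching group term. Report both contrasts for each antigen. State that staff stand in for the general population and that age is confounded with group (students are 3 to 21, staff 18 and over).
2. Describe λ as the persisting fraction. Compare modelled levels at named times within follow-up as well as k + log λ. State the unit of t and whether c is fixed or estimated.
3. Define t = 0 per antigen by type of exposure, since Goal 1 reads anti-NP as marking infection and anti-S without anti-NP as marking vaccination. Say how subjects with no datable exposure are handled. End a subject's segment at each recorded vaccination relevant to that antigen, each new PCR-positive episode and each confirmed large IgG rise. A new segment, if used, gets its own k.
4. State that vaccination dates, including those before enrolment, are captured. Contingency Plans says that vaccination will be recorded but does not mention dates.

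The cost is protocol and SAP wording and modest model code; no new sampling is needed. Segments become shorter and estimates less precise, mainly for λ, and subjects with no datable exposure may need separate handling.

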### Scientific Goal 3: Systems modeling to direct testing strategies

Our aim here is (A) to model potential transmission routes of COVID-19 at MCC using a network approach which can then be used to guide testing, and (B) to develop agent-based simulations to aid in developing and testing strategies to reduce risk of COVID-19 spread. We will pay particular attention to modeling how changes in vaccination rates and asymptomatic infection with low viral load (PCR cycle threshold – Ct) affect risk of transmission. These models will be used to define testing strategies and interventions to reduce the risk of COVID-19 spread in the Fall semester, and to explore the dynamic interplay between school operations, infection risks and control measures. *Successful completion of this work will result in development and deployment of generalizable simulation models to guide COVID-19 testing.*

*Network modeling* is ideally suited for analysis of risk of disease transmission in complex systems (1), and can account for symptom latency, changes in classroom group composition, and student mobility. Agent based models (ABMs) developed from network models can be used to study time varying outcomes arising from changes in behavior (e.g. vaccine acceptance), immunity, and asymptomatic infection among students, teachers and staff. This approach enables *in silico* evaluation of hypothetical testing strategies, simulation of infection dynamics, and assessment of alternative mitigation strategies. [name] has developed network models and analytics for risk of transmitted infection in a complex, high contact hospital environment (1), and [name] is currently creating ABMs that assess strategies to decrease COVID-19 infection risk on the UR Undergraduate Campus. Analytic approaches based on our prior work (1-6), will be used to construct (1) a network model of who is in contact with whom, for how long and (2) a mobility model of individual's travel between school locations and (3) agent based models of behavior, given data about anxiety, vaccine status, and adherence to guidelines. The **contact network**, will model testing strategies for surveillance for new infections in a mix of individuals with varying levels of immunity, vaccine acceptance, exposure, and new emerging viral strains. The **mobility network** will be used to model prevention strategies of changing staff and student classes/movement/interaction to decrease the risk COVID-19 transmission. **Agent based models** will test the effects of behaviors on school operations. The number of students and staff who remain on-site and in-school, will be key outcomes. Questions will include: How does the mixture of immunity, class/student scheduling, and vaccine acceptance create opportunities for COVID-19 spread (and control)? Do asymptomatic individuals with positive PCR tests spread virus?

*Network modeling* – We will contrast both a **contact network** and a **mobility network model (Fig 2)**. Data used for modeling will include the instruction schedules of IDD-students, staff and class locations. Each data record will contain the subject ID, activity, location, time, and duration. Student and staff attributes will be stored in the secure BLIS informatics database system (see Facilities and Resources), which will also hold the COVID-19 PCR and serology testing results. We will also incorporate anxiety data from the PROMIS survey (Goal 5 below), and rates of prior infection/vaccination (derived from serology data). We will use the schedule database to construct directed, bipartite graphs where the nodes represent two categories of individuals (students, staff), and the edges are weighted by the duration of contact (4, 6). A **mobility network model** (1, 2) (**Fig. 2B**) will capture the movement of students and staff between physical locations within the building. For both network models, we will characterize measures of network structure (density, diameter) (1, 4, 6), and identify individuals with high contagion centrality. We will simulate various testing frequencies of asymptomatic individuals (1). For example, we will model outcomes for increasing testing for: (1) staff who contact many students to decrease transmission risk, (2) staff who connect groups of students to decrease between-group spread. Sensitivity analysis will assess how modification of parameters (e.g. vaccination proportion, asymptomatic viral load) affects the ability to detect infection.

[figure not shown]

Figure 2

**Agent-based modeling** - ABMs are well-suited to dynamically characterize complex and difficult-to-measure mechanisms driving infectious disease transmission (7, 8). They are also used to design and evaluate interventions to reduce infection risks by simulation of "what-if" scenarios. MCC is an ideal setting for agent-based modeling as it is a circumscribed physical location with well-defined populations (i.e. students, staff), movement and interaction patterns. It is worth emphasizing that MCC is highly characteristic of the many similar school settings that provide services to children with IDD nationwide, and as such, provides an excellent test population form which to derive generalizable models. Agents will be individually characterized with fundamental attributes (e.g., movement rules, contacts with other agents, infection-susceptibility) that are abstract reflections of key variables (e.g. contact time, asymptomatic viral load, vaccine status). A wide range of use cases will be simulated including support for planning and deployment of testing procedures, exploring hypothetical testing or screening strategies, simulation of virus transmission dynamics, and assessment of alternative prevention or mitigation strategies. We will leverage guidance from administrators on student and staff activity schedules to study density and space in order to understand how they relate to possible patterns of infection. Simulations will examine the numbers of people in given rooms contemporaneously and the potential mixing of vulnerable and asymptomatically infected subjects. These efforts can inform the network models (see above) to guide decisions about when and who to test. The ABM models will be used to identify strategies to prevent negative impact of asymptomatic infected individuals, with logistical and/or financial constraints.

**Contingency Plans:** During COVID, MCC has had to respond to immediate changes in requirements from DOH and the NYS Governor. The process to "pivot" will be replicated, as it has worked well within the organization structure. Upon notification of a change, this will be broadly communicated to the project team, with same day conference established to evaluate and implement required changes. We anticipate during the course of this study that vaccinations will be approved for children under 16. This opportunity will be incorporated into educational initiatives, and will be recorded for study participants. Our scientific goals as outlined herein have built in contingencies around the expected introduction of vaccines in this population. We will also work with NIH program to revise the research and testing program in response to major changes in policy. The modeling goal described above is specifically designed to react to changing infection/vaccination landscapes.

**Community Partnerships and Engagement:** Our goal is to enroll 70% of eligible students and staff at MCC. This enrollment projection is based on past local experience of [name] and the MCC leadership, and the high motivation level of MCC parents/guardians and staff. To increase participant engagement and interest in the project we will modify our proposed student recruitment and retention approaches based on key input and feedback from MCC leaders and a convenience sample of parents/guardians (9, 10). Our approach will start with an Introduction Phase followed by an Engagement phase, concluding with a Consent phase that includes baseline (and follow-up) surveys to characterize the participants, their households and community of residence. The UR Clinical and Translational Science Institute (directed by MPI [name]) will assist, and has extensive experience in community engagement, recruitment and retention of special populations. The IDDRC Human Phenotyping and Recruitment (HPR) Core will also be leveraged for their expertise including recruiter training and retention strategies.

**Involvement of Community Stakeholders:** We will develop a full partnership with the MCC community that results in sustained community engagement across project activities, and also after the current project ends. In this context, the term 'community' includes: all students, their family members (including guardians), and all staff, affiliated with MCC. To do this, we have established the **Community Advisory Board (CAB)** to provide broad input on project design, implementation and iteration (see **Goal 1**).

**Strategies to Improve Testing and Vaccine Uptake; Communication Approach:** See **Goal 5**.

**Scientific Goal 4: Mobile Unit Testing:** We will staff, equip and deploy a customized, disability-enabled, mobile unit (*UR Health in Testing - HIT Mobile*) to bring testing directly to the MCC community.

Overview and Rationale: We have built a robust and trusting relationship with MCC, its leadership, staff, parents and students. A flagship component of this relationship is our UR-SMILEmobile, which provides specialized dental services to the IDD community. In 2020, the *SMILEmobile provided 280 visits and 927 treatments* to MCC children – thereby providing greater access to needed care.

The same considerations behind the creation of the *SMILEmobile* also apply to testing for COVID-19 (including access/mobility issues, limited agency and intellectual disability). The innovation of bringing care directly to MCC students has proven to be efficient, effective, and appreciated by MCC students, their parents, and the MCC staff. *A mobile COVID testing unit will add flexibility and scalability to testing at MCC, and will also enable testing at other remote locations.* For instance, if there were several positive test results in a nearby school or town, the mobile unit could be deployed to quickly test large numbers of students and staff *in situ*. This rapid response ‘hotspot’ testing will help identify people who are positive and reduce spread allowing schools to remain open without risking additional contamination. Positive subjects will be offered enrollment into the study to track dynamics and immunity.

[figure not shown]
Approach: We will staff, equip and deploy a customized, disability-enabled, mobile testing unit equipped with a specialized HEPA-filter enabled HVAC system (**UR Health in Testing - HIT Mobile**) that will directly deliver virological and serological testing to MCC students and staff on their campus. To do this, we will procure a customized van, designed to incorporate a wheel chair lift and seating for the driver, a nurse practitioner and a research assistant. The *HIT Mobile* will be smaller, simpler and more agile than the already successfully deployed SMILEmobile, since it does not require dental chairs or complex equipment, but will be designed for sufficient space to carry out testing. We have already sourced a number of vendors and solicited initial designs. A simpler design using a standard van and a pop-up medical tent (E-Z UP EMC100) will be implemented at study startup. This will permit initiation of the mobile testing unit approach within the first month after project approval. The custom van conversion will require several months to complete (anticipated in August 2021). The process will be initiated immediately upon project approval, in order to put a sustainable approach in place for the fall and winter months.

Testing strategy: We will use a blended approach to testing start-up, setting up initial testing in a dedicated room within the MCC building complex, but we will transition to outdoor testing using the on-site van and pop-up tent as available. We project that the mobile unit should be able to administer tests every 5-10 minutes for staff, and every 10-15 minutes for students, allowing between 40-80 tests/day.

Evaluation: *The goal of the mobile testing strategy is to demonstrate the generalizable value and utility of bringing testing directly to the IDD community, using an innovative, mobile approach. We hypothesize that this approach will increase engagement and uptake by the IDD community and school staff.* We will assess attitudes towards testing, use of the bus, and differences in testing turn-around/adoption between the in-school testing and the mobile unit as part of our program evaluation efforts.

Dissemination of Findings: Mobile units will expand services beyond MCC and can be replicated in other locations. They are sustainable and easy to maintain compared to on-site footprints which are often difficult to acquire, expensive and disruptive to existing workflows/classrooms. We will disseminate our findings in a methods paper and will also present them to the NYS 853 and 4410 Coalition of Schools.

**Scientific Goal 5: Overcoming Testing & Vaccine Hesitancy; Measuring Impact:** Major barriers to return-to-school efforts are driven by (mis)perceptions of risks related to virus infection, testing and vaccination by parents, guardians, and staff. Anxiety, stress and medical mistrust further add to testing and vaccine hesitancy, which is a particular concern in a setting where many of our at-risk children meet diagnostic criteria for autism spectrum disease (ASD). To address these issues, we will leverage our recent success in reducing vaccine hesitancy in our URMC staff, to design and implement educational and intervention strategies that mitigate these issues in the MCC community by addressing common myths, misconceptions and concerns about vaccination, testing and virus infection. Initial surveys of URMC staff in late 2020 (reflecting over 10,000 responses) revealed a disappointing 40% level of vaccine hesitancy. We addressed this with a major targeted educational outreach effort, tailored to specific staff populations. The result was an 85% uptake rate of the vaccine among the 20,000 plus URMC staff eligible to receive it in early 2021 – i.e., a

STUDY #: 5294

Version Date: 04/17/2023

Page 7 of 27

**60% reduction in the rate of vaccine hesitancy.** We will take a similar approach in the MCC community, as follows:

- 1) Conduct focus group interviews via zoom with priority populations to understand the nuances of COVID-related anxiety and vaccine hesitancy, and the locations/context that encourage greater vaccine acceptance.
- 2) Develop and deploy targeted strategies to increase understanding of the COVID-19 vaccine, that help individuals and communities make informed decisions about whether or not to receive the vaccine. This will require building and mobilizing a network of community partners, leaders and influencers, maximizing opportunities to build trust and share information.
- 3) Develop effective communication tools and platforms, including the preparation of materials in multiple languages, and the development of specifically targeted messaging for the MCC sub-communities and populations most impacted by COVID. Examples of these tools are: educational videos, testimonials, posters, digital and social media, web pages and public relations efforts.
- 4) Deliver on-the-ground education, including an educational speakers' bureau, accessible by online request, which will send speakers to community groups (via Zoom or other virtual platforms). Even more targeted activities in the form of individualized "table talk" conversations will be developed for families and other small groups to discuss the vaccine in trusted settings.
- 5) Create innovative visual media and art, in collaboration with the URMC's Artist in Residence. Specifically, we will use graphic medicine to address common myths, misconceptions and concerns about vaccines, as well as humanizing portraiture that creates visual narratives in which trusted peers and coworkers share their reasons for choosing to become vaccinated.

**Measuring Impact:** We will assess the impact of this program by deploying a validated, electronic outcome reporting scale that is already in widespread use across the UR health system (11), and at Rochester's East High School (12), to collect longitudinal data from staff, children (by proxy reporting) and parents/guardians across multiple health domains - including anxiety, depression, sleep disturbance, and social functioning (13). Specifically, we will customize the standard, short form Patient-Reported Outcomes Measurement Information System (PROMIS®-29) survey, by adding an additional domain to evaluate COVID-specific anxiety and vaccine hesitancy in our parent and school worker communities, based on concerns identified in our URMC staff baseline survey (see above) and in our initial MCC focus group interviews. We will then deploy the enhanced PROMIS-29 scale in electronic form within the MCC community, via two user-friendly approaches: (1) iPad/tablets at MCC (our standard approach in UR's ambulatory health clinics), and (2) mobile devices. We expect the latter approach to substantially increase survey participation, particularly among parents/children who have elected not to attend school, due to severe underlying health concerns, high levels of anxiety or other considerations.

Data collection takes < 5 mins with these approaches. All data will be stored on a secure, redundant, HIPPA-compliant server located behind the URMC's firewall. Participants will be sampled monthly using methods from our prior work at East High School (12) and the UR medical system (11). Each participant will receive a survey invitation unique to their email address or cell phone number, and surveys will be delivered in a self-report format (for MCC staff and parents) or in a proxy-report format (for children with IDD). In addition to the custom COVID-related survey domain, PROMIS-29 domains that we expect to be most informative will include the following: A) Anxiety, B) Depression, C) Sleep Disturbance and D) Social Functioning. We are especially interested in the relationship between generalized anxiety, COVID-specific anxiety and vaccine hesitancy – and how these parameters are influenced by the educational, interpersonal and art-based interventions that we will deploy. We are also interested in measuring the impact of in-person school attendance by MCC school children, on all of these domain areas (this will be analyzed by comparing the two cohorts of MCC school children who are currently attending the school in person, to the cohort who are participating in school programs on a 100% virtual/distance basis).

Our goal is to use the enhanced PROMIS-29 scale to determine if a highly effective COVID testing and containment/prevention program, based on cutting-edge data-driven modeling approaches, and combined with innovative educational outreach efforts, not only enables sustainable in-person school attendance, but also results in broad improvements in health outcomes for children and their families. Finally, in proposing to adapt and enhance the PROMIS-29 scale to this specific use case, and to develop generalizable models and educational interventions, we also intend to develop a scalable approach that can be readily disseminated and adapted to schools across the country.

STUDY #: 5294

Version Date: 04/17/2023

Page 8 of 27

**Confidentiality of Testing and other Data:** Identified data will be reported from the laboratory to the ordering provider ([name] at MCC) via secure fax. MCC will report results clinically, to the State via secure electronic channels, and to the county DOH for the purposes of guiding contact tracing and post-exposure testing. Individuals who are selected for post-exposure testing will NOT be informed of the identity of the individual to whom they may have been exposed. At UR, individual-level data will be made available only to a very limited number of persons in the modeling and intervention team, who will use the information exclusively to inform their modeling and infection control efforts.

